drop-in and drop-out rates low (e.g., rigorous training for active group vs. energized successful aging group promised free hearing aids at trial completion). Among 13 participants in the ACHIEVE-Pilot study who were randomized to the hearing intervention and have since been followed to 1 year, we did not observe any drop-out (discontinuation of hearing aid use) at 1 year (12 participants reported > 8 hours of hearing aid use/day and 1 participant reported 4-8 hours use/day). Similarly, drop-in rates will likely be minimized because all participants in the successful aging group are informed that they will receive free hearing intervention after 3 years of follow-up (out-of-pocket costs for hearing aids are otherwise currently ~\$4700 and are rarely covered by insurance). Rates of uptake of hearing aid use remain low in the community. In the HealthABC study among individuals with hearing loss in the inclusion range for the ACHIEVE study, rates of hearing aid uptake were ~3-4% per year.

- Missing data/withdrawal from competing events (e.g., mortality not associated with dementia): Estimated at 10%/year (corresponding to 27% in 3 years)

Based on these parameters and with 850 total individuals randomized, we will have 90% power to detect a 35% difference in annual cognitive decline between the hearing intervention vs successful aging intervention at 3 years follow-up.

**Aim 2:** For the secondary outcome of incident cognitive impairment, a dataset was constructed of participants in the ARIC cohort who had comparable characteristics to the individuals enrolled in ACHIEVE, did not exhibit signs of cognitive impairment at the baseline, and who were monitored over a period of 5 to 8 years. The observed rate was 50 cases of incident cognitive impairment per 1000 person-years. Assuming a 30% reduction in the hearing intervention condition and a 25% loss of person-time due to attrition, the planned analysis would have 80% power to detect a hazard ratio of 0.54 when using a 2-sided test and  $p < 0.05$ .

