ACHIEVE is a randomized, open-label trial comparing a hearing intervention versus a successful aging control intervention. The original plan for enrollment was to recruit 850 participants with approximately 425 in each condition. The final enrollment was expanded to 977 participants following a sample size assumption analysis (see section 5.2) conducted in June 2019. Enrollment began in November 2017. Each participant will be followed for 36 months; the COVID-19 pandemic made in-person visits impossible from mid-2020 to mid-2021 delaying the closeout 36 month visit for many participants.

Participants in the hearing intervention condition are fitted with a hearing aid, instructed to be worn on a daily basis for study duration, and attend four 1-hour intervention sessions spaced over the 2-3 months post-randomization. Re-instruction in use of devices and hearing rehabilitative strategies will be provided every 6 months.

The successful aging control intervention consists of four 1-hour intervention sessions spaced over the 2-3 months post-randomization focusing on participant-selected topics from the 10 KeysTM to Healthy Aging program and upper body stretching. Additional sessions will be provided every 6 months.

When spouses or cohabitating partners are both eligible and randomized together, they will be randomized as a unit with, arbitrarily, the first spouse/partner of the pair to be selected according to the random assignment procedure and the second spouse/partner of the pair receiving the same assignment. Spouse/partner pairs will be randomized in spouse/partner-pair specific permuted order blocks of varying sizes within strata defined by participant status (at least one spouse/partner pair in ARIC or both non-ARIC participants) and by field site.

Pre-screening will determine if an individual meets the inclusion criteria. The screening visit is used to consent participants and to determine if an individual meets audiometric, vision, and cognitive inclusion criteria. During the baseline visit assessments measures of primary and secondary outcomes will be collected.

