5.1 Preliminary Analysis

Data from the ARIC cohort, the Advanced Cognitive Training for Independent and Vital Elderly (ACTIVE) randomized trial, and the Health Aging and Body Composition (HealthABC) study were utilized to estimate that in the absence of an intervention a factor score (described in section 8.0) of global cognitive function would decline at a rate of 0.08 standard deviations (SDs) per year with a variability of 0.09 SDs. These estimates of the slope and variance were translated into expected values at Year 3. Power was conservatively estimated using a simplified t-test approach, while recognizing that greater power would be provided in the analysis of the primary outcome of cognitive decline through the application of repeated measures mixed effects models (described in section 7.3). The original sample size for ACHIEVE was 850, which provided greater than 90% power to detect a 35% difference in annual cognitive decline (Intervention: -0.052, Control: -0.08) with a 2-sided test and p < 0.05.

Attrition due to withdrawal or mortality was estimated at 10% per year, corresponding to 27.1% over 3 years. This is a conservative estimate given that *total* attrition in ACHIEVE is 6.7% as of October 6th, 2021. The drop-in/drop-out rate was estimated at 15% over 3 years. This rate reflects participants in the successful aging control condition who begin to wear hearing aids (drop-in) and participants in the hearing intervention condition who stop wearing hearing aids (drop-out). As of October 6th, 2021 there are 46 participants in the control condition who are currently using hearing aids (9.4% drop-in) and 8 participants in the intervention condition who are not currently using hearing aids (1.6% drop-out). After accounting for a 15% drop-in/drop-out rate, the difference at Year 3 was reduced to 29% (Intervention: -0.057, Control: -0.08). With an attrition rate of 10% per year, the initial sample size for ACHIEVE provided greater than 80% power to detect a difference utilizing a 2-sided t-test and p < 0.05.

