For the secondary outcome of incident cognitive impairment, a dataset was constructed of participants in the ARIC cohort who had comparable characteristics to the individuals enrolled in ACHIEVE, did not exhibit signs of cognitive impairment at the baseline, and who were monitored over a period of 5 to 8 years. The observed rate was 50 cases of incident cognitive impairment per 1000 person-years. Assuming a 30% reduction in the hearing intervention condition and a 25% loss of person-time due to attrition, the proposed proportional-hazards model (described in section 7.5) would have 80% power to detect a hazard ratio of 0.54 when using a 2-sided test and p < 0.05.

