7.7 Adjustment for Multiple Comparisons

Statistical significance for the primary outcome will be defined as p < 0.05. Secondary outcomes will be evaluated for statistical significance with a Hochberg modification to the Bonferroni adjustment, in which the p-values of the five outcomes will be ordered. The largest p-value will be compared relative to p < 0.05, and if met, all parameters will be considered significant. If not, then the second largest p-value will be assessed relative to p < 0.05/2 = 0.025, and if met then it and all other parameters will be considered significant, and so on for the 3rd p-value compared at 0.05/3=0.017, the fourth compared to 0.05/4 = 0.012, and the fifth compared to 0.05/5 = 0.01.

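### The 80% power for incident cognitive impairment is an unadjusted 0.05 figure; under the plan's own Hochberg rule it is about 58–73%, depending on the other outcomes

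*SAP*

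**What the plan says.** SAP 5.1 bases the power for incident cognitive impairment on ARIC data ("The observed rate was 50 cases of incident cognitive impairment per 1000 person-years") and on two planning assumptions ("Assuming a 30% reduction in the hearing intervention condition and a 25% loss of person-time due to attrition"). It concludes that the model "would have 80% power to detect a hazard ratio of 0.54 when using a 2-sided test and p < 0.05". Protocol 12.1, Aim 2, repeats the claim: "the planned analysis would have 80% power to detect a hazard ratio of 0.54 when using a 2-sided test". The sentence gives neither a sample size nor a follow-up time. The same section records that "The original sample size for ACHIEVE was 850".

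The decision rule is stated elsewhere, in SAP 7.7 and in the same words in Protocol 12.2: "Secondary outcomes will be evaluated for statistical significance with a Hochberg modification to the Bonferroni adjustment". Five p-values are ordered and compared with 0.05, 0.025, 0.017, 0.012 and 0.01, starting from the largest. The SAP change table for version 5.2 lists the five as global cognitive decline, time to incident cognitive impairment, and decline in memory, executive function and language. SAP 7.5, by contrast, counts four secondary outcomes.

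SAP 5.2 and Protocol 12.4 update the power to 80% at a hazard ratio of 0.60 with 977 participants, and give no alpha.

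**The concern.** The power sentence and the significance rule describe different tests. Under Hochberg, a p-value between 0.025 and 0.05 on the impairment outcome counts as significant only if every other outcome in the family is also below 0.05. Otherwise the outcome has to meet a stricter threshold, down to 0.01 in a family of five.

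The outcome is called an important secondary outcome, and SAP 7.5 commits its result to the primary manuscript. If it turns out not significant, a reader may weigh that result against the printed 80%, which the trial's own rule does not provide.

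**Working it through.** **Inputs.** Control rate 0.05 per person-year, 30% reduction and 25% of person-time lost (SAP 5.1). About 425 per arm (SAP 4: "recruit 850 participants with approximately 425 in each condition"). Follow-up of 3 years (SAP 4). Using N = 850 for this sentence is an inference from SAP 5.1, and using 3 years is an inference from SAP 4.

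**Events.** 425 × 3 × 0.75 × 0.05 × (1 + 0.70) = 81.3.

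**Reproducing the plan's figure.** Schoenfeld, 1:1 allocation: power = Φ(½·√events·|ln HR| − z), with z the two-sided critical value. At HR 0.54, ½ × √81.3 × 0.616 = 2.778. At 0.05, Φ(2.778 − 1.960) = 79.3%. The hazard ratio with 80% power is 0.537, which rounds to 0.54. The statement therefore reproduces, and it reproduces at unadjusted 0.05. Counting events under HR 0.54 itself (73.6 events) gives 75.3%, a poorer match.

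**Power at each Hochberg threshold.** The third column starts from exactly 80% at 0.05 (noncentrality 1.960 + 0.842 = 2.80). The last column uses N = 977: 977/2 × 3 × 0.75 × 0.05 × 1.70 = 93.4 events, and at HR 0.60, ½ × √93.4 × 0.511 = 2.469.

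| Threshold | 850, HR 0.54 | Any true 80% | 977, HR 0.60 |
|---|---|---|---|
| 0.05 | 79.3% | 80.0% | 69.5% |
| 0.025 | 70.4% | 71.2% | 59.0% |
| 0.0167 | 64.9% | 65.8% | 53.0% |
| 0.0125 | 61.0% | 61.9% | 48.8% |
| 0.01 | 58.0% | 58.9% | 45.7% |

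**Power under the full procedure.** Which threshold applies depends on the other outcomes, so Hochberg was simulated with 81.3 events, HR 0.54 and moderate correlation between outcomes:

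- Others null: 58% with five outcomes, 61% with four.
- Each of the others at 80% power: about 71–72% with five, 73% with four.

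Starting from exactly 80% and varying the correlation from 0 to 0.5 gives 59% and 62% with the others null. With the others at 80% power it gives 71–73% (five) and 73–75% (four).

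**Detectable effect at the floor.** exp(−2(z + 0.842)/√81.3) is 0.469 at 0.01 and 0.477 at 0.0125, against the stated 0.54.

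**The updated statement.** If 80% at HR 0.60 held at 0.05, the same column of the table puts its floor at 59–62%. With the SAP 5.1 inputs and 977 participants, power at HR 0.60 is about 70% unadjusted and 46–49% at the floor.

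**The case against.** The strongest reply is that nothing is miscalculated. The documents print the alpha beside the power, the figure reproduces at that alpha, and neither document claims that it holds under Hochberg. That stands: a reader might infer an arithmetic error, and there is none. What is missing is power under the rule that will be applied.

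Second, the floor is a corner case. It needs a hazard ratio of 0.54 on impairment together with no effect on global cognition or any domain. Protocol 7.3 builds MCI, and most dementia diagnoses, partly from decline on the same battery, so that combination is unlikely. This also stands, and it is why the range has to be given and not the floor alone. Even with every other outcome at 80% power, though, the loss is about 6 to 8 points from the reproduced 79%.

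Third, 850 was superseded. At 977 participants (93.4 events) and HR 0.54, unadjusted power is 85%. Hochberg power is 66–69% with the others null and 77–79% with the others at 80% power. The 25% loss of person-time is also a planning value; SAP 5.1 reports total attrition of 6.7% at October 2021. If the loss were 5% (an assumption), 977 participants would give 977/2 × 3 × 0.95 × 0.05 × 1.70 = 118 events, and power at HR 0.54 would be about 78% even at 0.01. A reader might infer that the trial as run has only about 60% power for this outcome. The documents do not support that.

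Finally, this figure did not size the trial. Protocol 12.1 bases the sample size on the primary outcome. That limits the consequence to how the secondary result is read.

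**Conclusion.** The concern holds as a mismatch between the stated power and the stated decision rule. The 80% at HR 0.54 is right at an unadjusted two-sided 0.05. Under the Hochberg rule, the same inputs give about 71–73% if the other outcomes each have 80% power, and a floor of about 58% (family of five) or 61% (family of four) if they have no effect. These figures rest on N = 850, 3 years of follow-up, events counted under the 30% reduction, proportional hazards, and moderate correlation between outcomes for the simulated values. The floor is a worst case at the original sample size, not the expected power of the enrolled trial. The updated sentences have the same gap and do not state an alpha. The point concerns reporting and interpretation; the validity of the planned test is not affected.

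**What to change.** In SAP 5.1 and Protocol 12.1, label the 80% as unadjusted and add the Hochberg range, for example: about 58–73%, depending on the other outcomes and on whether the family has four or five members. Settling the size of the family first would narrow the range.

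In SAP 5.2 and Protocol 12.4, state the alpha behind the 80% at HR 0.60 and add a Hochberg figure computed for 977 participants and that hazard ratio. The 58–61% floor must not be carried over, because it belongs to N = 850 and HR 0.54. The event count used there should be stated too, since the SAP 5.1 inputs give about 70% unadjusted and not 80%.

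The cost is a few sentences and less favourable figures. Sample size, endpoint, test and thresholds stay as they are.

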5.2 Evaluation of Assumptions

An assumptions analysis took place in June 2019, prior to the closure of the initial recruitment period. The goal of the analysis was to evaluate a subset of the assumptions described above and assess the value of a possible increase in the sample size. Since ACHIEVE was not going to be stopped early for efficacy or futility, regardless of the interim results, and the interim analysis only investigated assumptions around attrition and drop-in/drop-out rates, not outcomes, the interim analysis did not lead to increased type I error rates. Moreover, it was important to determine the extra required sample size, if any, as soon as possible in order to promptly begin the second stage of recruitment and expand the sample while there were still active participants from the initial stage.

Both the attrition rate and the drop-in/drop-out rate were examined based on 1 year follow-up data from approximately 200 participants. The data suggested that the original assumptions made in the sample size calculations were reasonable. However, there was potential variability in the estimates since partial data were used in the analysis. Consequently, the DSMB recommended increasing the sample size up to 1000 participants. The final sample size is 977 participants. This increased sample provided additional power for all tests, including greater than 90% power to detect a difference in cognitive decline after accounting for the estimated attrition and drop-in/drop-out rate as well as 80% power to detect a hazard ratio of 0.60 in the proportional-hazards analysis of incident cognitive impairment.

6. Analysis Populations

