7.5 Secondary Outcomes

An important secondary outcome is time until a composite of (1) adjudicated dementia determined from inperson or phone-based evaluations, (2) adjudicated MCI²⁶ determined from in-person evaluations (3) a 3point drop in the 30-item MMSE administered in-person, or (4) a 3-point drop in a factor score derived from the 10-item MMSE orientation subscale and 11-item Blessed scale administered over the phone and rescaled to be equivalent to the 30-item MMSE. Intervention conditions will be compared for the time until the composite outcome utilizing a discrete-time, cause-specific proportional-hazards model with a complimentary log-log link. The same baseline covariates specified for the mixed effects model will be integrated into the proportional-hazards model. Time on study will be the time scale. As a sensitivity analysis, we will examine variations of the composite outcome that include (1) adjudicated MCI from phone-based evaluations and (2) unadjudicated MCI diagnoses identified algorithmically. In exploratory analyses, we will analyze time until (1) adjudicated dementia or MCI diagnosis and (2) decline in MMSE and Blessed scores as separate events.

Three additional secondary outcomes that will be examined include decline in the cognitive domain factor scores for memory, executive function, and language¹⁴ derived from in-person assessments. Intervention conditions will be compared using the same statistical methods described above for the primary outcome. Results from the analysis of the four secondary outcomes will be included in the primary outcome manuscript.

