ACHIEVE completed randomization on October 25, 2019 prior to the outbreak of COVID-19. ACHIEVE suspended in-person research visits and began conducting only telephone contacts in March 2020. In July 2020 ACHIEVE initiated a modified version of the in-clinic neurocognitive battery which was collected over the telephone. For ACHIEVE participants who will become due for their final Year 3 study visit beginning in January 2021 while field site clinics are still closed, their final study visit will be a split visit that will comprise both a phone-based component (conducted at the time of their anticipated 36-month visit) AND an in-person component that will be conducted once field site clinics reopen in the future. At these in-person visits, all the data that are expected based on the 36-month visit per the protocol will be collected. There will be a minimum 3-month interval between the occurrence of a 36-month phone visit and when an in-person visit would be scheduled. For this reason some of the participants will have more than 36-months of follow-up time. Participants will be able to receive the other study intervention at the final in-person visit.

During the COVID-19 quarantine, some ACHIEVE participants may have made less use of their hearing aids and social isolation may have impacted their cognitive status. This has the potential to reduce any effect of the intervention.

10. Software and Statistical Programming

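### The 80% power quoted for a hazard ratio of 0.60 at 977 participants does not follow from the stated inputs, which give 0.56; the input behind 0.60 is not disclosed

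*SAP*

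**What the plan says.** For incident cognitive impairment, SAP 5.1 and Protocol 12.1 (Aim 2) take a rate of 50 cases per 1000 person-years from a comparable ARIC dataset. The remaining inputs are given as "Assuming a 30% reduction in the hearing intervention condition and a 25% loss of person-time due to attrition", with a two-sided test at 0.05. The result is 80% power for a hazard ratio of 0.54.

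SAP 5.2, repeated in Protocol 12.4, then describes the June 2019 evaluation and the increase to 977 participants. It states that "This increased sample provided additional power for all tests", and gives as one consequence "80% power to detect a hazard ratio of 0.60 in the proportional-hazards analysis of incident cognitive impairment". On the inputs it says "The data suggested that the original assumptions made in the sample size calculations were reasonable". In the sentence that carries the 0.60 figure, the power for the primary outcome is given "after accounting for the estimated attrition and drop-in/drop-out rate". No new event rate, person-time loss, follow-up or event count is attached to 0.60.

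Two other statements bear on the point. SAP 5.1, in the primary-outcome paragraph, notes that total "attrition in ACHIEVE is 6.7% as of October 6th, 2021". SAP section 9 notes that, because of the split Year 3 visit, "some of the participants will have more than 36-months of follow-up time". Neither is linked to the hazard-ratio calculation.

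**The concern.** A 15% larger sample moves a detectable hazard ratio only a little, because the detectable log hazard ratio shrinks with the square root of the number of events. A move from 0.54 to 0.60 is too large for that. Either 0.60 is wrong, or an input other than sample size was changed without being stated.

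The outcome matters. SAP 7.5 lists it first among the secondary outcomes: "An important secondary outcome is time until a composite". This sentence is the plan's only statement of what the enlarged trial could detect for it. As written, it credits the extra 127 participants with a gain that comes mostly from elsewhere, and it invites the reader to compare two hazard ratios that do not rest on the same assumptions.

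**Working it through.** **Inputs.** From SAP 5.1: control rate 0.05 per person-year; intervention rate 0.05 × 0.70 = 0.035; 25% of person-time lost; two-sided 0.05; 80% power. From SAP section 4: 850 planned and 977 enrolled, about equal arms, 36 months of follow-up. The hazard-ratio paragraph restates neither the sample size nor the follow-up, and the plan names no power formula. I used Schoenfeld's formula because it reproduces the plan's own 0.54.

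**Formulas.**
- Events: D = N × 3 × 0.75 × (0.05 + 0.035)/2 = 0.095625 × N
- Detectable hazard ratio at 80% power: HR = exp(−2 × 2.8016/√D), where 2.8016 = 1.960 + 0.842

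**Step 1: the plan's figure at 850.** D = 81.3 and HR = 0.537, which rounds to the stated 0.54.

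**Step 2: the same inputs at larger samples.**

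| N | Events | HR at 80% power |
|---|---|---|
| 850 | 81.3 | 0.537 |
| 977 | 93.4 | 0.560 |
| 1,000 | 95.6 | 0.564 |

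At N = 977, power at HR 0.60 is 69.5% with 93.4 events, or 66.8% if the event count itself assumes HR 0.60 (87.9 events). Even the 1,000-participant ceiling does not approach 0.60.

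**Step 3: a check without an event model.** At fixed power, the events needed scale as 1/(ln HR)².
- Ratio of events needed, 0.60 against 0.54: (ln 0.54/ln 0.60)² = 120.3/82.7 = 1.455
- With the most favourable rounding (0.545 to 0.595): 1.367
- Increase in sample: 977/850 = 1.149
- Unexplained factor: 1.455/1.149 = 1.27 (1.367/1.149 = 1.19 with favourable rounding)

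Rescaling the plan's own 0.54 by sample size alone gives exp(ln 0.54 × √(850/977)) = 0.563, or 0.558 to 0.568 if 0.54 stands for anything from 0.535 to 0.545. Reaching 0.60 through sample size alone would take 850 × 1.455 ≈ 1,237 participants, or about 1,162 with favourable rounding.

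**Step 4: other conventions.** The Freedman formula, an unequal-event variance, different bases for counting events, several attrition models, and one- and two-sided tests were also tried. None gave both 0.54 at 850 and 0.60 at 977. The two-sided versions that round to 0.54 at 850 give 0.56 to 0.57 at 977.

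**Step 5: what would produce 0.60 at 977.** Changing only the person-time loss, with three years of follow-up:

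| Person-time loss | Events | HR at 80% power |
|---|---|---|
| 25% (stated) | 93.4 | 0.560 |
| 6.7% | 116.2 | 0.595 (0.5947) |
| 3.4% | 120.3 | 0.600 |
| 0% | 124.6 | 0.605 |

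With the 25% loss kept, 0.60 needs a mean follow-up of about 3.9 years, or a control rate of about 64 per 1000 person-years.

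**The case against.** The best defence is that 0.60 is a sound figure with its inputs left out. SAP 5.1 reports total attrition of 6.7% and calls the planning value conservative. Attrition is not the same as lost person-time: if 6.7% leave evenly over follow-up, about 3.35% of person-time is lost, and 977 participants then give 120.4 events and a hazard ratio of 0.600. Alternatively, 6.7% taken in full as lost person-time, with an assumed mean follow-up of 3.1 years because of the delayed Year 3 visits, gives 120.1 events and again 0.600. On this view the gap is one of disclosure, and replacing 0.60 by 0.56 without qualification would reinstate a 25% loss that was far from what was observed. It can also be said that this is a retrospective sentence about a secondary outcome and that no decision depended on it.

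Much of this stands. 0.60 is reachable, and the consequences are limited. It does not rescue the text, however. Neither SAP 5.2 nor Protocol 12.4 mentions these inputs. Both credit the larger sample, report that the planning assumptions looked reasonable, and use the estimated attrition for the primary outcome in the same sentence. The evaluation they describe dates from June 2019 and used one-year data from about 200 participants, whereas the 6.7% is from October 2021. The halving is also uncertain: the planned 25% person-time loss lies close to the plan's 27.1% three-year attrition, which suggests that the authors may not have halved. If attrition was updated, the sentence mixes two attrition assumptions and attributes the gain to the wrong cause.

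**Conclusion.** The concern holds. Under the stated inputs, 977 participants give 80% power for a hazard ratio of 0.56, and power at 0.60 is 67% to 69%, at least 10 percentage points below the claim.

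These exact values rest on Schoenfeld's formula, three years of follow-up, and events counted at the 30% reduction. The conclusion that sample size cannot account for the change rests only on 0.54 referring to 850 participants and on the square-root relation between events and the log hazard ratio. Whether 0.60 is a miscalculation or the result of an undisclosed change of input cannot be settled from the documents; the sentence needs correcting either way. The primary sample size and primary analysis are not touched. This should be fixed, but it is confined to the power statement for a secondary outcome.

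**What to change.** In SAP 5.2 and Protocol 12.4, do one of the following:

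- give 0.56 as the hazard ratio detectable with 80% power, stated explicitly as holding under the section 5.1 assumptions; or
- keep 0.60 and state the input that changed, with the event count, person-time loss and mean follow-up used. For reference, about 3.4% person-time loss over three years gives 0.600, and 6.7% gives 0.595.

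If updated attrition was in fact used, the second option is the right one. In both cases, name the power formula. The cost is a text edit in two places, with no change to the model, thresholds, sample size or data.

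A separate reporting note, not part of the error: the event count assumes a 30% reduction, yet power at that effect (hazard ratio 0.70) is not given. Under the section 5.1 inputs it is about 36% at 850 and 41% at 977, or about 49% at 977 with 6.7% person-time loss. It would help to report this and to say whether the rate of 50 per 1000 person-years covers the full composite in SAP 7.5, since a higher composite rate would raise these figures.
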